10.5. Study Drug Accountability and Reconciliation

All patients will be expected to bring their bottles of study drug with them to all study visits (including empty bottles), unless a telephone visit, where patients will be asked to count the number of tablets remaining in their current bottles, document this on a form provided to patient, and return this form and study drug (with bottles) via courier to the site. At each study visit, the site staff will inspect the drug bottles, and perform a count of the tablets remaining in the bottles and document this in the patient's record. For telephone visits, drug accountability by the site staff will occur after the study drug is returned to the site via courier. For home visits (Week 14 or ET only), site staff will collect bottles and conduct accountability upon return to the site. An assessment of drug adherence should be done by the study staff to ensure that the patient understands all dosing instructions and is taking the drug as prescribed. Patients will be asked for an explanation if the count of returned study drug tablets indicates a discrepancy between the expected number of tablets dosed and the number returned in the bottles. If it is found that the patient is not taking the study drug as expected, the patient will be re-counseled with instructions, and this should be noted in the patients' records. A deviation should be recorded on any patient who is less than 70% compliant with dosing between visits and one of the Medical Monitors should be contacted.

Tonix or its designee will perform drug accountability which entails reconciliation between the amount of drug shipped to the study site, study drug assigned and dispensed to the patient (including returned unused assigned study drug), and study supplies that were never dispensed and/or assigned to patients.

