11.5.2. Early Termination (Post-Randomization)

In accordance with the Declaration of Helsinki, patients have the right to withdraw from the study at any time for any reason, and they will be advised of this right. The Investigator and Tonix also have the right to remove patients from the study. Specific reasons for removal of a patient from the study could include, but are not limited to:

- An AE
- An illness that, in the judgment of the Investigator or Tonix, might invalidate the study data or place the patient at risk
- The request of the patient, Investigator, or Tonix, whether for administrative or other reasons
- Pregnancy

Patients who wish to terminate their participation in the study should be instructed to come to the clinic for an Early Termination Visit. The purpose of the Early Termination visit is to obtain critical information about the patient's participation and should be scheduled preferably before there has been a substantial lapse in study drug usage. However, even if there has been a drug lapse, the patient should be encouraged to return to the clinic for this visit and should be instructed to return all study drug and bottles. NOTE: These visit procedures are not intended for patients who fail to qualify for randomization or for patients who withdraw from the study prior to receipt of a dose of double-blind study drug.

The following assessments and procedures are completed at this visit as ordered below:

- Document reason for early termination
- Assess changes in medication history and concomitant medications
- Assess study drug compliance (Telephone visit exception - patient will be instructed to count the number of tablets remaining in their current bottles, document this on a patient provided form, and return this form with the study drug (including bottles) to the site for assessment of compliance in a pre-paid pre-addressed courier envelope supplied in a "tele-visit" package to patient).
- Have patient complete the BDI-II
- Administer the "Since Last Visit" version of the C-SSRS
 - a. Results of the C-SSRS and BDI-II should be reviewed together to ensure (1) the patient is not experiencing suicidal ideation or worsening depression that requires intervention and (2) both scales are providing a consistent clinical picture of the patient with regard to suicidality. (Telephone visit exception – response to Question #9 of the BDI-II is reviewed with the patient and C-SSRS is administered over the phone).

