12.2.6. Diary Assessments

The daily diary is an important aspect of this study, and all patients must receive training explaining what is being asked of them, when to complete the diary, and how to use the diary system effectively. Patients will need to receive instructions and a password that uniquely identifies them when they log into the system along with instructions about what to do if they have difficulty completing the diary.

The diary should be started the evening of Visit 1 and completed daily until Visit 6 (Week 14). Patients should be instructed to complete the diary in the evening before dosing. Once the patient has properly identified themselves, the diary will prompt answers to the following:

- Rate your average pain during the past 24 hours on a scale from 0-10, where zero is no pain and 10 is worst possible pain.
- Rate your sleep quality last night on a scale from 0-10 where 0 is the best possible sleep and 10 is the worst possible sleep.

After randomization to study drug at Visit 2, the following questions will be added to the daily diary (starting in the evening of the day after randomization, Day 2):

- Did you take your study drug last night? (Yes/No)
- If yes, how many tablets of study drug did you take last night? (1 tablet/2 tablets)

The study staff will be expected to monitor patient adherence in completing the diary throughout the study, and will be instructed to call the patient should any problems or significant non-adherence be observed. During the screening period, there are diary compliance requirements that must be met in order for the patient to qualify for randomization. Patients who have been randomized should be encouraged to continue to complete their diary. Patients will receive a reminder to complete their diary if they miss diary entries. Patients who miss two diary entries will be flagged by the IRT system, and site staff will be alerted to contact patients for re-training and to instruct the patient on the importance of routine completion of their diary.

12.2.7. Assessment of Changes in Sexual Function: Changes in Sexual Functioning Questionnaire Short-Form (CSFQ-14)

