12.3 Exposure and Compliance

The treatment duration will be calculated and summarized based primarily on CRF data for first and last dose dates (number of days=last dose date - first dose date+1). If these values are missing or subjects' diary data indicate dates that exceed this period, the diary dates will be utilized.

Days of exposure will be based on subjects' responses to the daily questions regarding medication usage. The number of days on study drug is the total number of days a subject respond that study drug was taken. If the CRF data for the last dose date is a date not included in the diary, it will be added to the count (this should be true for most completing subjects since they do not fill out a diary the day of their last visit). The number of subjects with total exposure by visit weeks (≤ 2 weeks, 2 to ≤ 4 , 4 to ≤ 8 , 8 to ≤ 12 , 12 to ≤ 14 and >14 weeks) will be presented. Missing days where the subject did not complete the diary will be treated as though study drug was not taken. Days of exposure will also be calculated for the days on each dose of study drug.

Additionally, the number and percentage of subjects that drop back to one tablet per day will be summarized and the week in which they reduced their dose will be tabulated (among those that had a dose reduction).

Compliance will be similarly summarized across all study visits for each treatment arm. Study drug compliance as a percentage will be defined as the exposure days defined above divided by the total number of expected days on treatment multiplied by 100. The expected number of days will be the date of last diary recorded dose-randomization date +1. This compliance reporting

will take into account whether or not they took any medication, but will not account for the number of tablets they took on a given day.

Compliance will be summarized with descriptive statistics by treatment arm. The number and percentages of subjects within certain categories of compliance (e.g. < 60%, 60% to < 80%, 80% to <= 100%, greater than 100%) will also be presented.

A listing of drug accountability data based on CRF data will be provided.

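### SAP 12.3 ends expected dosing days at the last diary-recorded dose, so a patient who lapses off drug but stays to Visit 6 or ET can be reported as fully compliant

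*SAP*

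**What the plan says.** SAP 12.3 defines compliance as "exposure days defined above divided by the total number of expected days on treatment multiplied by 100". The numerator comes from the diary: "The number of days on study drug is the total number of days a subject respond that study drug was taken", with one addition: "If the CRF data for the last dose date is a date not included in the diary, it will be added to the count". Unfilled diary days are handled strictly: "Missing days where the subject did not complete the diary will be treated as though study drug was not taken". The denominator is then fixed by one sentence: "The expected number of days will be the date of last diary recorded dose-randomization date +1". It does not refer to Visit 6, ET, Day 98 or the last diary entry, and neither document gives another denominator for this percentage.

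The protocol allows for lapses. Section 11.5.2 says the ET visit "should be scheduled preferably before there has been a substantial lapse in study drug usage". Section 10.5 has tablets counted at visits and non-adherent patients re-counselled, and adds: "A deviation should be recorded on any patient who is less than 70% compliant with dosing between visits". SAP 9.2 summarizes deviations by type and treatment group. SAP 12.3 also summarizes treatment duration and exposure by week band, and lists the accountability data.

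**The concern.** Expected days should be the nights on which the patient was due to take drug. Here the patient's own last dose sets the end of the count. A gap in mid-study lowers the score, while an equal gap at the end removes itself from the denominator. The strict rule for unfilled diary days is undone in the same way, because such days after the last recorded dose are not counted either.

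The primary endpoint is read from the final diary week. Under SAP 8.1.2 anyone with 14 weeks of diary pain data is analysed as a completer, and under SAP 8.1.3 imputation applies only to missing scores. A patient who has lapsed but still fills in the diary therefore contributes observed Week 14 pain. A reader who turns to the compliance table to learn whether such patients were taking drug near the endpoint gets an answer that leaves out the nights in question.

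**Working it through.** The documents state no compliance figure to reproduce, so the SAP rule is applied to hypothetical patients.

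**Inputs.** Randomization is Day 1 and dosing runs Days 1–98 (SAP 4.2). Visits 5 and 6 fall nominally on Days 71 and 99 (Protocol 11.4, 11.5.1). Week 14 is Days 92–98 (SAP 8.2.1). The evening diary asks about the previous night's dose (Protocol 12.2.6), so the Week 14 entries follow nights 91–97. Each patient takes every dose until stopping and completes the diary through Day 98.

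**Formulas.**
- SAP compliance = (diary Yes nights, plus 1 if the CRF last dose is not in the diary) ÷ (last diary-recorded dose day − 1 + 1).
- Planned-period compliance = nights dosed ÷ 98.
- Between-visit compliance = doses on nights 71–98 ÷ 28.
- Exposure in weeks = exposure days ÷ 7.

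| Last dose | SAP 12.3 | Planned period | Visit 5 to 6 | Exposure band |
|---|---|---|---|---|
| Night 56 | 56/56 = 100% | 56/98 = 57.1% | 0/28 = 0% | 8.0 weeks: 4 to ≤8 |
| Night 77 | 77/77 = 100% | 77/98 = 78.6% | 7/28 = 25.0% | 11.0 weeks: 8 to ≤12 |
| Night 90 | 90/90 = 100% | 90/98 = 91.8% | 20/28 = 71.4% | 12.9 weeks: 12 to ≤14 |
| Night 98 (full completer) | 98/97 = 101.0% | 98/98 = 100% | 28/28 = 100% | 14.0 weeks: 12 to ≤14 |

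**Coherence.** One later dose lowers the score:
- Stop after night 77, then dose on night 97: 78/97 = 80.4%, down from 100%.
- Stop after night 56, then dose on night 97: 57/97 = 58.8%, down from 100%.

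Placing the 21 missed nights in mid-study instead of at the end gives 77/97 = 79.4%.

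**Earlier gaps.** With six missed nights before stopping at night 56, the SAP gives 50/56 = 89.3%, against 50/98 = 51.0%. The score is exactly 100% only if nothing was missed before the lapse.

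**What escapes the other checks.** On nominal visit days the 70% line is 0.70 × 28 = 19.6 doses, so 20 doses pass. A last dose on night 90 just passes, stays in the completers' exposure band, and leaves all seven Week 14 entries following nights off drug.

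**Other readings of the denominator.** If the date is that of the diary entry, one night later, the night-77 patient scores 77/78 = 98.7%, which changes nothing of substance. If it meant the last dosing answer, Yes or No, the same patient would score 77/97 = 79.4%. The wording refers to a recorded dose, so it does not support that reading, and a patient who stopped both drug and diary would still score 100%.

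**The case against.** The strongest reply is that other outputs show the lapse. For longer lapses this stands. Last doses on nights 56 and 77 fall far below 70% between visits, reach the by-arm deviation summary, and sit in a lower exposure band than completers. A reader might infer from the compliance rule that late lapses are invisible throughout the report; the documents do not support that. They are missing from this percentage. For the night-90 case the reply fails: the two checks do not separate that patient from a completer, which leaves the treatment-duration figure and the by-patient accountability listing.

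A second reply is that ending at the last dose is a deliberate on-treatment measure. For patients who formally discontinue, that is a reasonable choice, and their 100% is not an error in itself. But the SAP does not state this purpose or limit the rule to such patients.

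A third reply is that the current rule protects patients who keep dosing but stop filling in the diary. This stands as a cost of any change. A nightly doser whose last entry is Day 77 has 76 recorded doses plus the CRF last dose, so a 98-night denominator gives 77/98 = 78.6%, the same as a patient who truly lapsed after night 77.

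**Conclusion.** The concern holds for one group: patients who lapse without being recorded as discontinuing and who remain to Visit 6 or ET. For them the percentage is overstated by dropping the whole final gap, for example 100% instead of 78.6% after a last dose on night 77. The figures assume a complete diary, no earlier gaps and nominal visit days. The documents give no frequency for such lapses and no basis for assuming that they differ by arm.

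A reader might infer that the primary result is affected. The documents do not support this. The primary analysis is ITT, SAP 7 defines no per-protocol population, and compliance enters no planned efficacy model. The 70% line in Protocol 10.5 applies between visits and should not be set against a whole-study percentage. The fault lies in descriptive reporting and is worth correcting because it can hide a missed endpoint week.

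**What to change.** Replace the denominator sentence in SAP 12.3:

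- Expected days are every night from randomization through the night before Visit 6 or ET.
- For patients recorded as discontinuing study drug, expected days run through discontinuation, and that figure is labelled on-treatment compliance.
- The same percentage is reported for the nights covered by the Week 14 diary week (nights 91–97 on the nominal schedule). The night-90 patient would then show 0/7 = 0%.
- The number of missing-diary nights, or the tablet-count compliance, is shown beside the new figure, because it understates compliance for patients who keep dosing but stop the diary.

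If the current figure is kept, label it *compliance through last recorded dose*.

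On nominal visit days the change also brings the full completer from 98/97 to 98/98. It costs a short text change and a small program change, using visit dates, diary answers and tablet counts already collected. SAP 12.3 names CRF first and last dose dates but no separate discontinuation date, so confirm which field supplies it. Reported compliance can look less favourable; the primary analysis is unchanged.

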13. CHANGES FROM PLANNED ANALYSIS

The protocol inadvertently omitted the in-clinic pain assessments from the list of exploratory endpoints; it was added to this SAP.

15. APPENDICES

15.1 Appendix A

| Fatigue 8a | | |
|------------------------------------|----------------|------------|
| Short Form Conversion Table | | |
| Raw Score | T-score | SE* |
| 8 | 33.1 | 4.8 |
| 9 | 38.5 | 2.7 |
| 10 | 41.0 | 2.2 |
| 11 | 42.8 | 2.0 |
| 12 | 44.3 | 1.9 |
| 13 | 45.6 | 1.8 |
| 14 | 46.9 | 1.8 |
| 15 | 48.1 | 1.8 |
| 16 | 49.2 | 1.8 |
| 17 | 50.4 | 1.8 |
| 18 | 51.5 | 1.7 |
| 19 | 52.5 | 1.7 |
| 20 | 53.6 | 1.7 |
| 21 | 54.6 | 1.7 |
| 22 | 55.6 | 1.7 |
| 23 | 56.6 | 1.7 |
| 24 | 57.5 | 1.7 |
| 25 | 58.5 | 1.7 |
| 26 | 59.4 | 1.7 |
| 27 | 60.4 | 1.7 |
| 28 | 61.3 | 1.7 |
| 29 | 62.3 | 1.7 |
| 30 | 63.3 | 1.7 |
| 31 | 64.3 | 1.7 |
| 32 | 65.3 | 1.7 |
| 33 | 66.4 | 1.7 |
| 34 | 67.5 | 1.7 |
| 35 | 68.6 | 1.7 |
| 36 | 69.8 | 1.8 |
| 37 | 71.0 | 1.8 |
| 38 | 72.4 | 2.0 |
| 39 | 74.2 | 2.4 |
| 40 | 77.8 | 3.7 |

*SE = Standard Error

15.2 Appendix B

| Sleep Disturbance 8a Short Form Conversion Table | | |
|---|----------------|------------|
| Raw Score | T-Score | SE* |
| 8 | 28.9 | 4.8 |
| 9 | 33.1 | 3.7 |
| 10 | 35.9 | 3.3 |
| 11 | 38.0 | 3.0 |
| 12 | 39.8 | 2.9 |
| 13 | 41.4 | 2.8 |
| 14 | 42.9 | 2.7 |
| 15 | 44.2 | 2.7 |
| 16 | 45.5 | 2.6 |
| 17 | 46.7 | 2.6 |
| 18 | 47.9 | 2.6 |
| 19 | 49.0 | 2.6 |
| 20 | 50.1 | 2.5 |
| 21 | 51.2 | 2.5 |
| 22 | 52.2 | 2.5 |
| 23 | 53.3 | 2.5 |
| 24 | 54.3 | 2.5 |
| 25 | 55.3 | 2.5 |
| 26 | 56.3 | 2.5 |
| 27 | 57.3 | 2.5 |
| 28 | 58.3 | 2.5 |
| 29 | 59.4 | 2.5 |
| 30 | 60.4 | 2.5 |
| 31 | 61.5 | 2.5 |
| 32 | 62.6 | 2.5 |
| 33 | 63.7 | 2.6 |
| 34 | 64.8 | 2.6 |
| 35 | 66.1 | 2.7 |
| 36 | 67.5 | 2.8 |
| 37 | 69.0 | 3.0 |
| 38 | 70.8 | 3.2 |
| 39 | 73.0 | 3.5 |
| 40 | 76.5 | 4.4 |

*SE= Standard Error on T-score metric
Adult version

15.3 Appendix C

The following conventions will be used for calculation of a subject’s nominal Week 14 score. All other week scores are calculated relative to the nominal Week 14 interval.

| Landmark Endpoint Visit Day | Last Available Diary Score Recorded | Days Used to Calculate “Week 14” | Comment |
|------------------------------------|--|---|--|
| 99 | 98 | 92-98 | Ideal condition with final study visit on Day 99, last diary data will be day 98. |
| 100 | 99 | 93-99 | |
| 101 | 100 | 94-100 | |
| 102 | 101 | 95-101 | |
| 103 | 102 | 96-102 | |
| 104 | 103 | 97-103 | |
| 105 | 104 | 98-104 | |
| 106 | 105 | 99-105 | |
| Out of window (late) | 106+ | 99-105 | Since the Week 14 endpoint is Day 99 +/- 4 days, days after 106 are outside the Week 14 nominal interval. Any scores recorded after day 106 will be ignored. |
| 98 | 97 | 91-97 | |
| 97 | 96 | 90-96 | |
| 96 | 95 | 89-95 | |
| 95 | 94 | 88-94 | |
| 94 | 93 | 87-93 | Out of window, but allowed |
| 93 | 92 | 85-92 | Out of window, but allowed |
| 92 | 91 | 85-91 | Out of window, but allowed |

| | | | |
|-----|-----|-----|--|
| <92 | <91 | 85+ | Must have a valid score occurring on/after day 85 or will be missing for week 14 |
|-----|-----|-----|--|

15.4 Appendix D

The following list of numbers will be used for random seeds where required for MI processes:

9179445

2389546

9954263

5612645

2599732

7189411

6986208

6225777

5483414

8849556

These will generally be used in order for the primary analysis, then secondary endpoints and sensitivity analyses. For cases where identical code may be applied to more than one outcome, the second to last digit will be incremented by 1 to produce new seeds for the subsequent outcome. If a single dataset requires more than the 10 seeds above, additional seeds will be generated by incrementing the last digit in the last by 1. In no case will the same seed be used in more than one procedure; all seeds used will be documented in the programming specifications and the programs themselves.

15.5 Appendix E

The following reporting conventions will be adopted for the presentation of study data. These conventions will enhance the review process and help to standardize presentation with common notations.

15.5.1 General Reporting Conventions

- All tables and data listings will be developed in Landscape Orientation, unless presented as part of the text in a clinical study report (CSR).
- Figures will be presented in Landscape Orientation, unless presented as part of the text in a CSR.
- Legends will be used for all figures with more than one variable or item displayed.
- Figures will be in black and white, unless color figures have been identified as useful for discriminating presentation in the figure. Lines in figures should be wide enough to view the line after being photocopied.
- Specialized text styles, such as bolding, italics, borders, shading, superscripted and subscripted text will not be used in tables, figures, and data listings unless they add significant value to the table, figure, or data listing.
- Only standard keyboard characters should be used in tables and data listings. Special characters, such as non-printable control characters, printer specific, or font specific characters, will not be used on a table, figure, or data listing. Hexadecimal character representations are allowed (e.g., μ , α , β).
- All titles will be centered on a page. The ICH numbering convention is to be used for all tables, listings, and graphs (TLGs).
- All footnotes will be left justified at the bottom of a page. Footnotes must be present on the page where they are first referenced. Footnotes should be used sparingly and must add value to the TLG. If more than four footnote lines are planned then a cover page may be used to display footnotes.
- Missing values for both numeric and character variables will be presented as blanks in a table or data listing. A zero (0) may be used if appropriate to identify when the frequency of a variable is not observed.
- All date values will be presented as YYYY-MM-DD (e.g., 2001-08-01) format. A four-digit year is preferred for all dates.
- All observed time values will be presented using a 24-hour clock HH:MM:SS format (e.g., 01:35:45 or 11:26). Seconds should only be reported if they were measured as part of the study.
- Time durations will be reported in mixed HHhr MMm SSs notation (e.g., 5h 32m, or 27h 52m 31s). The use of decimal notation to present (display) time durations should be avoided (e.g. 0.083h = 5m) unless it is necessary to show the computation of time

differences in a table, figure, or data listing, in which case both notations may be used to display the time duration.

- All TLGs will have the name of the program and a date stamp on the bottom of each output.

15.5.2 Population Summary Conventions

- Population(s) represented on the tables or data listings will be clearly identified in the last title of the Table as “<name of population>” and will be identical in name to that identified in the protocol or SAP.
- Consistent terminology will be used to define and identify a population. Common nomenclature may include (a) All Subjects, (b) ITT, (c) Safety, and (d) PP.
- Sub-population(s) or special population(s) descriptions will provide sufficient detail to ensure comprehension of the population (e.g., ITT >60 years of age) used for analysis in a table or figure.
- Population sizes may be presented for each treatment or dosing category as totals in the column header as (N=xxxx), where appropriate.
- Population sizes shown with summary statistics are the samples sizes (n) of Subjects with non-missing values.
- All population summaries for categorical variables will include all categories that were planned and for which the subjects may have had a response. Percentages corresponding to null categories (cells) will be suppressed.
- All population summaries for continuous variables will include: n, mean, SD, minimum, and maximum. Other summaries (e.g. number missing, median, quartiles, 95% confidence intervals, CV or %CV) may be used as appropriate.
- All percentages are rounded and reported to a single decimal point (xx.x%). A percentage of 100% will be reported as 100%. A percentage of zero will be reported as 0.
- Population summaries that include *P* values will report the *P* value to three decimal places with a leading zero (0.001). All *P* values reported on default output from statistical software (i.e., SAS[®] Software) may be reported at the default level of precision. *P* values <0.001 should be reported as <0.001 not 0.000.
